16.1.2 General Specifications for PK Concentration and PK Parameter Data

PK concentration samples taken before the first drug administration (predose samples) will be assigned a time of 0 hours, as if the sample had been taken simultaneously with the study intervention administration.

In case pre-dose samples have been taken after the subsequent dosing, the resulting concentrations will be included in concentration listings but excluded from descriptive statistics of concentrations and from PK parameter estimation. For post-dose samples collected outside the allowed time window, the resulting concentrations will be included in descriptive statistics of concentrations and in PK parameter estimation.

Values below the lower limit of quantification (BLQ) will be taken as zero for summary statistics of PK concentration data, PK parameter estimation (e.g., AUC) and for graphical presentations.

In case profiles have a measurable pre-dose concentration less than or equal to 5% of its C_{max} value, the participant's data will be included in the PK and statistical analyses without any adjustments. If the pre-dose value is greater than 5% of the C_{max} , the participant's data for this period will be included in the PK evaluation but excluded from descriptive and further statistical evaluation after agreement with the sponsor.

Missing concentrations (e.g., no sample, insufficient sample volume for analysis, no result or result not valid) will be reported and used generally as "N.R.". A participant who withdraws prior to the last planned observation will be included in the analyses up to the time of discontinuation.

PK concentrations which are erroneous due to a sampling processing or analytical error (as documented in the bioanalytical report) may be excluded from the PK analysis if agreed by the Sponsor.

PK concentrations and PK parameters excluded from summary statistics will not be included in mean figures.

If less than 3 post-dose concentrations are available within a PK profile, derived PK parameters will be flagged and might be excluded from statistical evaluation after consultation with the Sponsor.

16.1.3 Estimation of Pharmacokinetic Parameters

The computer program Phoenix® WinNonlin® version 6.4, or higher (Certara, L.P., Princeton, New Jersey, USA) will be used to derive PK parameters applying non-compartmental analysis (NCA).

The statistical software SAS® (Statistical Analysis System, SAS-Institute, Cary NC, USA, windows version 9.4 or higher) may be used to generate additional PK parameters, produce tables, listings and figures.

16.1.3.1 Estimation of Pharmacokinetic Parameters in Whole Blood

PK parameters will be calculated using the nominal elapsed time since dosing and QC'd bioanalytical data sets.

The following M5717 and pyronaridine whole blood PK parameters will be calculated where appropriate:

Symbol	Definition
AUC _{0-∞}	The area under the concentration-time curve (AUC) from time zero (dosing time) extrapolated to infinity, based on the predicted value for the concentration at t _{last} , as estimated using the linear regression from λ _z determination. AUC _{0-∞} = AUC _{0-t_{last}} + C _{last pred} /λ _z
AUC ₀₋₂₄	The AUC from time zero (dosing time) to 24 hours post dose. Calculated using the mixed log linear trapezoidal rule (linear up, log down) using the nominal dosing interval.
CL/F	The apparent total body clearance of study intervention following extravascular administration. CL/F = Dose p.o. /AUC _{0-∞} .
C _{max}	Maximum observed concentration
t _{1/2}	Apparent terminal half-life. t _{1/2} = ln (2)/λ _z
t _{max}	The time to reach the maximum observed concentration collected during a dosing interval (unless otherwise defined, take the 1st occurrence in case of multiple/identical C _{max} values)
Vz/F	The apparent volume of distribution during the terminal phase following extravascular administration. Vz/F = Dose/(AUC _{0-∞} *λ _z) following single dose.
λ _z	Terminal first order (elimination) rate constant. Determined from the terminal slope of the log-transformed concentration curve using linear regression on terminal data points of the curve.
AUC ₀₋₂₄ /Dose	The dose normalized AUC from time zero to 24 hours post dose. Normalized using the dose, using the formula AUC ₀₋₂₄ /Dose.
AUC _{0-t_{last}}	The AUC from time zero (= dosing time) to the time of the last quantifiable concentration (t _{last}), calculated using the mixed log-linear trapezoidal rule (linear up, log down).

AUC _{0-t_{last}} /Dose	The dose normalized AUC from time zero to the last sampling time (t_{last}) at which the concentration is at or above the lower limit of quantification. Normalized using the dose, using the formula $AUC_{0-t_{last}} / Dose$.
AUC _{0-∞} /Dose	The dose normalized AUC from time zero extrapolated to infinity. Normalized using dose, using the formula $AUC_{0-∞} / Dose$.
C _{max} /Dose	The dose normalized maximum concentration. Normalized using the dose, and the formula $C_{max} / Dose$

Additional PK parameters may be calculated where appropriate.

Units for PK parameter output will be based on concentration and dose units used in the study, unless otherwise specified. In case concentration data units change within the study, PK parameters will be reported using consistent units throughout study outputs.

The parameters C_{max} , and t_{max} will be obtained directly from the concentration-time profiles. If C_{max} occurs at more than one timepoint, t_{max} will be assigned to the first occurrence of C_{max} .

In cases BLQ concentrations occur at the end of the collection interval, these concentrations might be set to missing for calculations of partial AUCs after agreement with the Sponsor. This is an exemption to the general BLQ handling rule and should be applied in case its application would result in estimation of implausible partial AUC values. Implausibility is considered in cases partial AUCs were greater than $AUC_{0-∞}$.

The following PK parameters will be calculated for diagnostic purposes and listed, but will not be summarized:

- First ($λ_z$ low) and last ($λ_z$ up) time point of the time interval of the log-linear regression to determine $λ_z$.
- Number of data points ($Nλ$) included in the log-linear regression analysis to determine $λ_z$.
- Goodness of fit statistic (adjusted R^2) for calculation of $λ_z$.
- Span ratio of interval over which $t_{1/2}$ was estimated/ $t_{1/2}$
- AUC from time t_{last} extrapolated to infinity given as percentage of $AUC_{0-∞}$. ($AUC_{extra\%}$).

The regression analysis should contain data from at least 3 different time points in the terminal phase consistent with the assessment of a straight line on the log-transformed scale. Phoenix WinNonlin “best fit” methodology will be used as standard. If warranted, further adjustment may be made by the pharmacokineticist, after agreement with the Sponsor. The last quantifiable concentration $>LLOQ$ should always be included in the regression analysis, while the concentration at t_{max} and any concentrations BLQ which occur after the last quantifiable data point $>LLOQ$ should not be used.

If $AUC_{extra\%}$ is $> 20\%$, the coefficient of correlation (Rsq adj) of λ_z is < 0.8 , or the observation period over which the regression line is estimated (span ratio) is less than 2-fold the resulting $t_{1/2}$, the rate constants and all derived parameters (e.g., $t_{1/2}$, $AUC_{0-\infty}$, CL etc.) will be listed and included in the parameter outputs.

For calculation of dose-related parameters, no dose adjustment is required since dose administered is expressed as the free base dose.

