	
3. After the study intervention period (i.e., after the last dose of study intervention is administered) for <math>\geq 62</math> days, corresponding to the time needed to eliminate any study intervention(s) (5 terminal half-lives of 155 hours) plus 30 days (a menstrual cycle) after the last dose of study intervention (and agree not to donate eggs [ova, oocytes] for reproduction during this period). The Investigator evaluates the effectiveness of the contraceptive method in relationship to the first dose of study intervention. The Investigator reviews the medical history, menstrual history, and recent sexual activity to decrease the risk for inclusion of a female with an early undetected pregnancy.

Informed Consent	
7. Capable of giving signed informed consent, as indicated in Appendix 2, which includes compliance with the requirements and restrictions listed in the ICF and this protocol.

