16.1.4.1 Listings and Tables

- Individual concentrations and descriptive statistics of concentrations by analyte, and group
- Individual PK parameters and descriptive statistics of PK parameters by analyte, and group
- Individual dose normalized PK parameters and descriptive statistics of dose normalized PK parameters by analyte, and group
- Individual diagnostic PK parameters by analyte, matrix, day and group

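### The SAP's three reliability limits for the terminal slope have no effect: values that breach them are summarised unmarked, so profiles that end early can distort half-life, AUC0-inf, CL/F and Vz/F

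*SAP*

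**What the plan says.** SAP 16.1.3.1 lists the slope diagnostics (regression interval, number of points, adjusted R-squared, span ratio, percentage of AUC extrapolated). These "will be calculated for diagnostic purposes and listed, but will not be summarized". It then names three limits: extrapolated AUC above 20%, adjusted R-squared below 0.8, and a span below two half-lives. When one is breached, the rate constant and everything derived from it "will be listed and included in the parameter outputs".

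Three other places settle what that means in practice:
- SAP 16.1.1 (Descriptive Statistics of PK Parameter Data) summarises all non-missing values, and SAP 16.1.4.1 plans "Individual PK parameters and descriptive statistics of PK parameters by analyte, and group".
- The PK Analysis Set in SAP 8.1 has no criterion on the slope.
- SAP 16.1.2 keeps early leavers: "A participant who withdraws prior to the last planned observation will be included in the analyses up to the time of discontinuation".

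The SAP does attach a consequence to a different weakness. Under SAP 16.1.2, parameters from profiles with fewer than three post-dose concentrations are flagged and may be left out. The only half-life in either document is in Protocol 5.1, where contraception is timed from "5 terminal half-lives of 155 hours".

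**The concern.** A reliability limit is useful only if crossing it changes something. Here a half-life from a poor fit counts in the geometric mean exactly as one from a good fit, and the reader of the summary table cannot tell how many such values it holds.

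The values most at risk come from profiles that end early. After 72 h the next PK sample is Day 8 (168 h), so a profile ending there takes its slope from 48, 72 and 168 h, when the faster distribution phase may still contribute. The fitted half-life is then too short, the extrapolated tail too small, AUC0-inf low and CL/F high. Because Vz/F divides the dose by AUC0-inf times lambda_z, it moves as well.

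PK of both drugs is a stated secondary objective in Part A and Cohort B0. Protocol 4.2 intends the PK data in adolescents as a basis for later studies in younger children.

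**Working it through.** **Inputs.** Half-life 155 h (Protocol 5.1, not tied to one of the two drugs). Late PK samples on Days 8, 15, 22, 29 and 43 (Protocol Table 1), which is 168, 336, 504, 672 and 1008 h. Earlier samples end at 48 and 72 h (Protocol Table 2). At least three points in the slope regression (SAP 16.1.3.1).

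**1. The plan's own figure.** 5 x 155 / 24 + 30 = 62.3 days, which agrees with the 62 days in Protocol 5.1.

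**2. Do profiles pass at 155 h?** With a one-phase decline, the extrapolated share is 2^(-t_last/155). The span is the interval of the last three samples divided by 155, which is the worst case.

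| Last sample | Extrapolated | Span | Result |
|---|---|---|---|
| Day 43 | 1.1% | (1008-504)/155 = 3.25 | pass |
| Day 29 | 5.0% | (672-336)/155 = 2.17 | pass |
| Day 22 | 10.5% | (504-168)/155 = 2.17 | pass |
| Day 15 | 22.3% | (336-72)/155 = 1.70 | fail |
| Day 8 | 47.2% | (168-48)/155 = 0.77 | fail |

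With a Day 43 sample, the half-life must exceed 1008 x ln2/ln5 = 434 h to breach the 20% limit, or (1008-504)/2 = 252 h to breach the span limit on the last three samples. For assumed half-lives of 100, 155, 200, 300 and 600 h, extrapolation at Day 43 is 0.1, 1.1, 3.0, 9.7 and 31.2%.

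**3. What does an early end do to one profile?** Noise-free two-phase decline, terminal half-life 155 h, linear-up/log-down AUC, slope by best adjusted R-squared. The following are assumptions, not in the documents: absorption rate 0.7/h, distribution half-life 10-36 h, distribution phase carrying 60-80% of the initial level.

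| Profile ends | Distribution half-life | Fitted half-life | AUC0-inf | Span |
|---|---|---|---|---|
| Day 8 | 10 h (60%) | 140 h | 4% low | 120/140 = 0.86 |
| Day 8 | 15 h | 90-119 h | 10-14% low | 1.0-1.3 |
| Day 8 | 24-36 h | 63-95 h | 13-15% low | 1.26-1.91 |
| Day 15 | 24-36 h | 79-131 h | not used here | 2.01-3.95 |
| Day 43 | 24-36 h | 154-155 h | nearly unchanged | above 4 |

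- CL/F is dose divided by AUC0-inf, so at Day 8 it is 1/0.96 = 1.04 to 1/0.85 = 1.18 times the true value.
- Vz/F scales as half-life divided by AUC0-inf. That gives (140/155)/0.96 = 0.94 in the mildest case and (63/155)/0.87 = 0.47 in the most severe.
- Every Day 8 profile breaches the span limit. The four Day 15 profiles pass all three limits (extrapolation 5-15%) although their half-life is too short. The span is divided by the fitted half-life, so a falsely short one inflates it.

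**4. What does that do to a group summary?** If 3 of 12 Part A profiles ended at Day 8 (an assumption), the geometric mean is exp((9 ln155 + 3 ln x)/12). For x = 70 to 90 h this is 127-135 h instead of 155 h.

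**5. Would dropping the failures cure it?** 4,000 simulated profiles per row. Assumptions: distribution half-life 15 h, 60% of AUC in the terminal phase, 30% CV on half-life, 15% assay error. Entries are the geometric-mean half-life relative to truth.

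| Scenario | All profiles | Passing only |
|---|---|---|
| All complete, 155 h | 0.99 | 0.98 |
| 20% end Day 8, 155 h | 0.83 | 0.88 |
| 20% end Day 15, 155 h | 0.93 | 0.91 |
| 20% end Day 22, 155 h | 0.99 | 0.95 |
| All complete, 300 h (35% fail) | 0.99 | 0.85 |
| All complete, 434 h (69% fail) | 0.97 | 0.71 |

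In these rows the group AUC0-inf stayed within about 2% of truth either way. Dropping failures improved half-life only for Day 8 truncation. Elsewhere it moved the estimate further from truth.

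**The case against.** The best defence is that keeping every value is a deliberate and defensible choice. The diagnostics are listed for each participant, so weak fits can be found. SAP 16.1.3.1 also asks for three points on a straight terminal line and lets the pharmacokineticist adjust the fit with the sponsor's agreement, and parameters are calculated only where appropriate. In the 24-36 h model, the distribution phase supplies 32-66% of the 48 h concentration, so a careful analyst might report no half-life for a Day 8 profile. Step 5 shows that excluding failures can do harm.

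Much of this stands. It rules out exclusion as the main summary, and it means that the Day 8 errors in step 3 are what an unsupervised best-fit rule would give. It does not rescue the present text. Adjustment by judgement is optional, the listed diagnostics do not reach the summary table, and the stated rule is to include the value.

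A reader might go further and infer that the reported parameters are biased by truncated profiles, that truncation follows treatment failure, and that it distorts a comparison of Part A with Cohort B0. The documents do not support this:
- Sampling is planned to Day 43, and no number of early-ending profiles is given.
- Protocol 6.8.1 links rescue either to stopping study drug or to leaving the study, and Protocol 7.1 keeps those who stop study drug in follow-up. SAP 15.1.2 notes that a single dose cannot be stopped, so what happens to rescued participants is left open rather than shown to be withdrawal.
- Withdrawals get a closing visit where possible (Protocol 7.2), and the Day 29 visit that stands in for it includes PK sampling.
- The 2.5-40% in Protocol 2.3.1 is a model prediction of early failure, not a dropout rate. SAP section 7 says that the study stopped for compelling efficacy and safety.
- SAP section 7 drops comparisons between treatment groups, and SAP 9.1 presents the two cohorts separately.

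**Conclusion.** The point holds as a defect in the rule, with a conditional consequence. The SAP defines three limits for lambda_z and gives them no effect, so lambda_z, half-life, AUC0-inf, CL/F and Vz/F from failing fits are summarised unmarked.

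Complete profiles at 155 h are essentially untouched. A profile ending at Day 8 can return a half-life of about 63-140 h, AUC0-inf 4-15% low and CL/F about 4-18% high. These figures rest on the assumed two-phase decline and an automatic best-fit slope. The effect on a group depends on how many profiles end early, which the documents do not give, and on a half-life that they do not state separately for each drug. The AUC0-inf error is per affected profile and largely averages out when few are affected; half-life is the more exposed parameter.

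These are secondary, descriptive endpoints. The primary endpoints (safety in Part A, PCR-adjusted ACPR in Cohort B0) are unaffected. A breach signals an unreliable estimate and does not by itself prove bias.

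**What to change.** In SAP 16.1.3.1, replace the sentence that includes failing values without comment by a rule with three parts:
- Flag lambda_z, t1/2, AUC0-inf, AUC0-inf/Dose, CL/F and Vz/F from any profile that breaches a limit.
- Report the number flagged by analyte and group, and which limit was breached.
- Give the descriptive statistics of these parameters with and without flagged values, with equal standing, beside AUC0-tlast, AUC0-24 and Cmax.

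Do not make the summary without flagged values the main one. The span and extrapolation limits selectively remove genuinely long half-lives and miss some profiles that end at Day 15. AUC0-tlast needs no slope but also falls when a profile ends early, so AUC0-24 and Cmax are the steadier companions.

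The cost is a few sentences in the SAP and one extra table. The summary without flagged values will have a smaller n, possibly much smaller for an analyte with a long half-life. Two summaries that agree show that the results do not hinge on weak fits. If they differ, the flag counts show the reader why.

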## 1 Protocol Summary

### 1.1 Synopsis

**Protocol Title:** Phase IIa Proof of Concept, Multicenter, Randomized, Open-label Study to Evaluate the Safety, Efficacy, and Pharmacokinetics of the Combination M5717 plus Pyronaridine Administered once Daily for 1 or 2 Days to Adults and Adolescents with Acute Uncomplicated *Plasmodium falciparum* Malaria

**Short Title:** Phase IIa Proof of Concept Study of M5717-Pyronaridine in Adults and Adolescents with acute uncomplicated *Plasmodium falciparum* Malaria

**Rationale:** Artemisinin-based combination therapies (ACTs) have been the gold standard for acute uncomplicated *P. falciparum* malaria, but the increasing reports of emergent resistant strains to artemisinin-related compound therapies makes it necessary to look for new therapeutic tools. In this context, the current study intends to explore in a Proof of Concept the safety, preliminary efficacy, and pharmacokinetics (PK) of M5717 (free base) in combination with pyronaridine (tetraphosphate). An ACT containing combination pyronaridine-artesunate (Pyramax) will be used as internal control, mainly for safety purposes.

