M5717 is a first-in-class compound with a new mode of action (i.e., inhibition of plasmodial protein synthesis) and showed excellent activity against malaria blood stage (including clinical isolates and drug-resistant strains), liver-stage, and in transmission blocking assays in preclinical investigations. M5717 displayed a long half-life and an effective exposure with high potency against all forms of the parasite. This allows for administration of a single oral dose and maintaining protection over an extended period of time. A Phase I FIH study with an IBSM model demonstrated in laboratory isolates of *P. falciparum* that M5717 cured all 8 participants treated with a dose of 800 mg M5717 succinate (equivalent to 660 mg of the M5717), while lower doses were able to clear parasitemia, but recrudescence was observed in 3 out of 6 participants in the 150 mg cohort and in 2 out of 8 participants in the 400 mg cohort.

Pyronaridine was first used in China for the treatment of malaria as a single agent and later has been developed as a fixed-dose combination with artesunate which is currently registered in more than 25 countries and marketed in several countries as Pyramax: a fixed-dose combination of pyronaridine tetraphosphate and artesunate administered once a day for 3 consecutive days (180 mg/60 mg for the tablets and 60 mg/20 mg granules for oral suspension for the pediatric formulation) with a total daily dose depending on pre-defined weight bands with 720 mg/240 mg as maximum daily dose ([Croft 2012](#)). As of July 2021, more than 2 million patients have received Pyramax treatment worldwide. Pyronaridine is a molecule with blood stage activity that has to date shown no signs of resistance in the field.

Pyramax clinical efficacy and safety was demonstrated for acute uncomplicated *P. falciparum* malaria through 2 Phase II and 3 Phase III studies, as well as 1 Phase IIIB and 1 Phase IV study focused on the safety of the combination. A beneficial effect of Pyramax was established in the 2 pivotal Phase III studies (Africa, South-East Asia) in patients weighing > 20 kg and non-inferiority to established treatments could be shown. A single 3-day treatment course of Pyramax was generally well tolerated in the clinical studies. However, the clinical study data showed that a slightly higher number of patients experienced a transient mild to moderate increase in transaminases compared to the reference treatments.

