## **3              Objectives and Estimands**

### **Part A: Safety/Pharmacokinetics Run-in Cohort**

Part A of the study will explore the safety and PK of a single dose of M5717 of 330 mg given in combination with pyronaridine tetraphosphate (360 mg) in adult participants with acute uncomplicated *P. falciparum* malaria. Efficacy will be evaluated as a secondary objective. Doses in Part B of the study may be adjusted based on the exposure and safety data collected in Part A.

Please note that if endpoints refer to specific timepoints, the timepoints given refer to days after treatment. Thereby, time of treatment start is defined to be on Day 1. Consequently, if an endpoint defines the measurement to be taken, e.g., 7 days after treatment, this means that the measurement is actually taken on Day 8.

**Table 3** Objectives, Endpoints, and Estimands Part A

Objectives	Estimands/Endpoints	Ref. #
Primary		
To evaluate the safety and tolerability of the M5717-pyronaridine combination in adult participants with acute uncomplicated malaria due to P. falciparum	
Endpoint: Incidence, severity, and seriousness of study intervention-related TEAEs, as per CTCAE v 5.0
 
Additional endpoints related to safety and tolerability up to Day 29 (<math>\pm</math> 2 days): laboratory assessments, ECGs, and vital signs.
	1
Secondary		
To characterize the PK of M5717 and pyronaridine in adult participants with acute uncomplicated malaria due to P. falciparum	
Endpoint:
 
 
PK profiles for M5717 and pyronaridine
 
PK parameters of M5717 and pyronaridine such as <math>AUC_{0-t_{last}}</math>, <math>AUC_{0-\infty}</math>, <math>AUC_{0-24}</math>, <math>C_{max}</math>, <math>t_{1/2}</math>, <math>t_{max}</math>, CL/F, Vz/F, when data permits
 
	2

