## 4.2 Scientific Rationale for Study Design

The intent is to develop a 1- or 2-day dosing regimen of the M5717-pyronaridine combination. The approach in this study to define the doses to be used is based on considerations of safety and efficacy for these 2 dosing regimens.

The highest chance to show whether this combination is efficacious requires evaluating the highest therapeutic monotherapy doses in combination for both compounds. For pyronaridine, the highest approved dose in patients  $\geq 65$  kg is 720 mg daily in a 3-day treatment regimen. Therefore, 720 mg is the highest daily dose and has been selected for the 1-day (total dose 720 mg) and the 2-day dosing regimens (total dose 1,440 mg). This permits maintaining a reasonable safety margin compared to the 3-day Pyramax dosing regimen (total dose 2,160 mg).

Considering that this drug combination is administered to humans for the first time, Part A will investigate the safety and exposure after a single-day administration of an intermediate dose of 330 mg M5717 and 360 mg pyronaridine tetraphosphate in a group of 12 adults with acute uncomplicated *P. falciparum* malaria. This dose has been derived from half of the dose that showed a clinically relevant therapeutic effect as a single dose in previous studies (Blood Stage VIS); the outcomes of this study part will help to confirm the assumptions in terms of safety and exposure and decide whether dose adaptations are required for Part B.

Only adults will be recruited in Part A of the study, permitting to collect PK data that will help to understand if the exposure is matching with the predictions. In addition, risk of progression to severe malaria due to the potential lower efficacy of intermediate doses is expected to be lower in an adult population than in adolescents, who are immunologically better prepared to manage the infection ([Long 2017](#), [Maurizio 2019](#)).

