## 6.5 Dose Modification

A single daily dose 660 or 500 mg M5717 is selected as the dose to be evaluated in Cohort B0/B1 and a daily dose of 660 or 500 mg will be administered daily for 2 days in Cohort B2 (see [Table 5](#)). After completion of Part A, and after completion of Cohort B0, the IDMC will have the option to recommend a dose adjustment for M5717 based on the exposure deviation from the predicted exposure, that will be supported by internal PK/PD analysis. This is planned to avoid unnecessary under or overexposures in any of the doses assigned across the two weight bands established.

**Table 5** M5717 Free Base Dosage for Part A and B (Cohorts B0/B1 and B2)

Body Weight	Part A		Part B			
	Equivalent Dose	Treatment Regimen	Cohort B0/B1		Cohort B2	
			Equivalent Dose	Treatment Regimen	Equivalent Dose	Treatment Regimen
Adolescents ≥ 24 to < 45 kg	NA	NA	500 mg	Daily for 1 day	500 mg	Daily for 2 days
Adolescents ≥ 45 kg	NA	NA	660 mg	Daily for 1 day	660 mg	Daily for 2 days
Adults	330 mg	Daily for 1 day	660 mg	Daily for 1 day	660 mg	Daily for 2 days

NA=not applicable.

The pyronaridine dose in Cohorts B0/B1 and B2 will be a maximum daily dose of 720 mg pyronaridine for participants with body weight ≥ 65 kg and will be adjusted to the weight bands as specified for Pyramax in the SmPC ([Pyramax SmPC](#), see [Table 6](#)). This dose of pyronaridine will be given together with M5717 on a daily basis for a single day (Cohort B0/B1, in total 720 mg) or for 2 days (Cohort B2, in total 1,440 mg).

**Table 6** Pyronaridine Tetraphosphate Dosage for Part A and B (Cohorts B0/B1 and B2)

Body weight	Part A		Part B			
	Number of Tablets and Dose	Treatment Regimen	Cohort B0/B1		Cohort B2	
			Number of Tablets and Dose	Treatment Regimen	Number of Tablets and Dose	Treatment Regimen
≥ 24 to < 45 kg	2 tablets = 360 mg/day	Daily for 1 day	2 tablets = 360 mg/day	Daily for 1 day	2 tablets = 360 mg/day	Daily for 2 days
≥ 45 to < 65 kg	2 tablets = 360 mg/day	Daily for 1 day	3 tablets = 540 mg/day	Daily for 1 day	3 tablets = 540 mg/day	Daily for 2 days
≥ 65 kg	2 tablets = 360 mg/day	Daily for 1 day	4 tablets = 720 mg/day	Daily for 1 day	4 tablets = 720 mg/day	Daily for 2 days

A daily dose of Pyramax of a maximum of 720 mg pyronaridine and 240 mg artesunate will be given in Cohort B3 for 3 consecutive days according to the SmPC ([Pyramax SmPC](#), see [Table 7](#)).

**Table 7** Pyronaridine-artesunate (Pyramax) Dosage for Part B (Cohort B3)

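### SAP 16.1.3.1 waives dose adjustment because doses are free base; that is true for M5717, but the protocol gives the pyronaridine dose as tetraphosphate salt

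*SAP*

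**What the plan says.** SAP 16.1.3.1 opens its parameter table for both drugs: "The following M5717 and pyronaridine whole blood PK parameters will be calculated where appropriate". The section closes on dose basis with a sentence that names no analyte: "For calculation of dose-related parameters, no dose adjustment is required since dose administered is expressed as the free base dose".

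The protocol treats the two drugs differently:

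- The synopsis rationale sets the two bases side by side: "M5717 (free base) in combination with pyronaridine (tetraphosphate".
- Section 6.5, Table 5 is titled "M5717 Free Base Dosage for Part A and B (Cohorts B0/B1 and B2", while Table 6 is titled "Pyronaridine Tetraphosphate Dosage for Part A and B (Cohorts B0/B1 and B2".
- Section 3 describes Part A as M5717 "in combination with pyronaridine tetraphosphate (360 mg) in adult participants".
- Section 4.2 repeats it: "an intermediate dose of 330 mg M5717 and 360 mg pyronaridine tetraphosphate".
- Section 2.2 attaches the 180 mg Pyramax tablet strength to the salt: "a fixed-dose combination of pyronaridine tetraphosphate and artesunate administered once a day for 3 consecutive days (180 mg/60 mg for the tablets".

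Neither document gives a free-base pyronaridine dose, a salt factor or a molecular weight for pyronaridine. Protocol 8.4 says the whole-blood assay is validated, but not whether pyronaridine results are expressed as base or as salt.

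**The concern.** The SAP makes no adjustment because it takes the dose to be free base already. By the same reasoning, a dose stated as a salt would need converting before it is combined with base concentrations. Pyronaridine is dosed as a salt, and the section contains no exception for it.

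CL/F and Vz/F for pyronaridine are named secondary PK parameters, for Part A (SAP 5, endpoint 2) and for Cohort B0 (endpoint 34). Dose-normalised parameters are to be listed and summarised for each analyte (SAP 16.1.4.1). A reader who relied on 16.1.3.1 would take all of these as free-base values. If that is wrong, a comparison with base-expressed pyronaridine values from elsewhere would be off by a constant factor.

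**Working it through.** **Step 1: which parameters use dose.** SAP 16.1.3.1 lists 13 parameters. Six contain the dose:

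- CL/F = Dose / AUC0-∞ and Vz/F = Dose / (AUC0-∞ × λz), both proportional to the dose entered.
- AUC0-24/Dose, AUC0-tlast/Dose, AUC0-∞/Dose and Cmax/Dose, all inversely proportional to it.

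The other seven (the three AUCs, Cmax, tmax, t½, λz) do not use dose.

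**Step 2: is the pyronaridine dose base or salt?** Every protocol statement of basis quoted above says tetraphosphate. The tablet counts in Table 6 agree with the 180 mg strength in Section 6.1: 2 × 180 = 360, 3 × 180 = 540 and 4 × 180 = 720 mg. For M5717 the protocol does convert (Section 4.3 equates 660 mg with 800 mg succinate), so the free-base statement is right for that drug.

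**Step 3: size, if the assay reports base.** The plan has no figure of its own to reproduce. Two assumptions come from outside the documents: the salt carries four phosphoric acid units of 97.994 g/mol, adding 4 × 97.994 = 391.98 g/mol; and the base weight is M.

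Factor = (M + 391.98) / M

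| Assumed M (g/mol) | Factor on CL/F and Vz/F | Factor on dose-normalised values (1/factor) |
|---|---|---|
| 400 | 791.98/400 = 1.980 | 0.505 |
| 450 | 841.98/450 = 1.871 | 0.534 |
| 518 | 909.98/518 = 1.757 | 0.569 |
| 600 | 991.98/600 = 1.653 | 0.605 |
| 700 | 1091.98/700 = 1.560 | 0.641 |

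At 518 g/mol, CL/F and Vz/F come out 76% high and the dose-normalised values 43% low. Over the whole range they come out 56% to 98% high and 36% to 49% low.

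Base equivalents at 518 g/mol are 360/1.757 = 205 mg, 540/1.757 = 307 mg and 720/1.757 = 410 mg.

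**Step 4: size, if the assay reports tetraphosphate equivalents.** Dose and concentration are then on the same basis, and the factor is 1.0.

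**Step 5: reach.** The factor is one constant for every participant, so it cancels in any comparison of Part A with Cohort B0. It concerns one analyte in at most 12 + 25 = 37 planned participants.

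**The case against.** The strongest reply is that the sentence was written for M5717 and merely lacks the drug's name, since elsewhere the documents use the term free base only for M5717. That may well explain how it arose, but nothing in 16.1.3.1 limits it, and the section covers both analytes. If it is read as M5717 only, the SAP has no dose-basis rule for pyronaridine, and the same sentence still needs editing.

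A second reply is that the assay may report salt equivalents. This stands as regards size: the numerical error could be nil. The stated premise about the dose would still be wrong for pyronaridine.

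A third reply is that no harm within the study is shown, and this largely stands. The parameters are descriptive, and neither document plans to use the non-compartmental CL/F or Vz/F of pyronaridine in modelling or sets them against external values. Protocol 6.5 gives the IDMC's dose-adjustment option for M5717 on the basis of exposure and keeps the pyronaridine maximum daily doses fixed by weight band. Only CL/F and Vz/F, not the dose-normalised four, are named in the endpoints.

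A reader might infer that the trial will report pyronaridine clearance 1.76-fold too high. The documents do not support that as a fact, because they give neither the base weight nor the basis of the assay results.

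**Conclusion.** The concern holds as a minor inconsistency of dose basis between SAP and protocol. The reason given for making no adjustment is correct for M5717 and incorrect for pyronaridine; that conclusion needs nothing beyond the two documents.

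The numerical consequence is conditional. With base-expressed concentrations, CL/F and Vz/F are overstated by a factor of about 1.76 at an assumed 518 g/mol (1.56 to 1.98 over 700 down to 400 g/mol), and the four dose-normalised parameters are understated by the same factor. With salt-expressed concentrations there is no error.

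Nor should a reader carry the point further than this. Pyronaridine AUC, Cmax, tmax and half-life, all M5717 PK, efficacy, safety and the Part A versus B0 comparison are unaffected on either assumption.

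**What to change.** In SAP 16.1.3.1:

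1. Limit the no-adjustment sentence to M5717.
2. Confirm from the bioanalytical report whether pyronaridine concentrations are expressed as base or as tetraphosphate, and state this in the SAP.
3. If base, multiply the administered tetraphosphate dose by the base/salt molecular-weight ratio, with the ratio written into the SAP, before computing CL/F, Vz/F and the four dose-normalised parameters. At minimum, label those outputs as based on the tetraphosphate dose.
4. If salt equivalents, keep the salt dose and label the outputs accordingly.

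The cost is a sentence or two in the SAP and at most one constant in the pyronaridine dose input. No new samples or data are needed, and any affected output already produced can be corrected by a single scale factor.
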